### 6.3 Observation period

#### 6.3.1 Inclusion period

The gynaecologist will choose the patients as they go to the clinic and meet the inclusion and exclusion criteria, according to the consecutive sampling technique. The assignment of the study treatment will be randomised,

depending on the previously-established code that will be assigned to each patient as they are included in the study. A recruitment period of 4 months and a follow-up period of 3 months are planned. Recruitment of participating centres will be competitive.

### 6.3.2 Follow-up period

Follow-up will be 3 months from the inclusion visit ( $V_0$ ). Patients should attend two control visits in person and answer two telephone interviews.

### 6.3.3 Baseline Visit – $V_0$ (inclusion)

After the case history and initial examination, which will serve to substantiate the suspicion of VV due to infection, patients will be recommended to participate in the trial provided they meet the inclusion/exclusion criteria. Once the patient Information Sheet (PIS) has been handed over, the patient has signed the Informed Consent (IC) form and the investigator has verified that the patient meets the inclusion and exclusion criteria, they will proceed to fill in the CRF baseline visit sections.

During this first visit, socio-demographic data, relevant clinical history and gynaecological history will be recorded. The investigator will assess the patient's symptoms by recording the presence of clinical signs and symptoms of infectious VV (stinging, itching, erythema, oedema, abnormal vaginal discharge, etc.) and the *Sobel score* (see section 7.0). The vaginal pH determination test will then be carried out and the samples for the different laboratory tests will be collected, which will consist of: spreading the vaginal discharge sample on a slide to subsequently count the *Lactobacillus spp.* and collecting the discharge sample with a swab that will also be used for the diagnostic confirmation culture and for the fresh vaginal smear. The samples will be stored properly according to the instructions specified in the manual of use of the sampling kit until the samples are collected.

The patient will be given the treatment corresponding to the code assigned to her, reminding her that she has the possibility of changing treatment group, at the time that she deems appropriate. If the assigned treatment is ineffective or

is not tolerable, the patient may contact the hospital to bring the first control visit forward and request a change of treatment.

During the baseline visit, the patient will be given a CRF which she must fill in and return at the end of the visit and a card with a link to the online home CRF (Patient diary) that must be filled in over the course of the study. The home CRF will be used to monitor the patient during the follow-up weeks. The home CRF may also be delivered on paper and the patient must deliver it later.

The investigator will give the patient product for one treatment cycle (which may range from 3 days (Clindamycin) to 7 days (boric acid 150 mg, *L. gasseri*, *L. rhamnosus*)).

The patient must return the empty blisters and/or surplus product during the first control visit. One week after the baseline visit, the patient will be contacted by telephone to find out her condition and if she is responding to the treatment, to assess the need for a rescue treatment or to arrange the first control visit. The first in-person control visit ( $V_1$ ) will be carried out at least 2 weeks after the treatment has been completed.

#### 6.3.4 Control telephone contact a week after starting the treatment:

The investigator will contact the patient and will proceed with a brief questionnaire to decide whether the patient responds correctly to therapy depending on the symptoms the patient will describe and their severity. The different options in this scenario are:

Patient condition	Investigator's action
Disappearance of symptoms	In-person appointment ( $V_1$ ) within two weeks of the telephone contact and the end of the treatment (21 days from $V_0$ ).
Improvement of symptoms, but the patient still has mild clinical signs and symptoms	In-person appointment ( $V_1$ ) within two weeks of the telephone contact and the end of the treatment (21 days from $V_0$ ); we recommend that she request an appointment if there is no improvement in the following days. If there is a suspicion that there is still an

	infection, rescue treatment will be recommended.
Deterioration/Lack of effectiveness	The patient must arrange an appointment as soon as possible to proceed with the alternative rescue treatment.

Depending on the investigator's criteria, an appointment will be made with the patient for an in-person visit. When making an in-person appointment, the investigator will take into account the date of the patient's last menstruation to prevent it from coinciding with the patient's 1st control visit. To this end, the investigator may slightly extend the 2-week margin previously established between the call and the control visit.

#### 6.3.5 1st Control Visit ( $V_1$ )

The second in-person visit of the study will be carried out approximately two weeks after completing the treatment.

As with  $V_0$ , the investigator and the patient will have a CRF that they must fill in. The investigator will record the data regarding the clinical examination and repeat the tests and collect the samples corresponding to  $V_1$ . The results of the analytical tests carried out during  $V_0$  will also be recorded.

The patient will fill in the corresponding CRF and return it at the end of the visit. An approximate time and date will be specified for the follow-up telephone interview around 2 months after the inclusion and an appointment will be made for the final follow-up visit (3 months from the patient's inclusion in the study).

If the investigator suspects a potential lack of effectiveness of the assigned treatment, rescue with the other therapeutic alternative of the study may be suggested according to the aetiology of the VV. In the event of crossing treatments, this visit will be considered the new baseline visit ( $V_0$ ), for the purpose of collecting data and samples. The same procedure will be followed if the second visit is brought forward at the patient's request.

### 6.3.6 Telephone interview (TI) 8 weeks after the inclusion

Approximately 8 weeks after the baseline visit, the investigator will telephone the patient to interview her, with the main objective of knowing if there are signs of recurrence of VV.

The patient will confirm whether she is regularly filling in the online CRF and that she is not taking/using any products that may interfere with the assessment of the study objectives (see section 6.2.4: Discontinuation criteria).

The investigator will fill in a short form as a summary of the interview and confirm the appointment for the third and last in-person visit (V2). The patient will be reminded that, if the home CRF is completed on paper, she must deliver it during the last visit.

### 6.3.7 2nd Control Visit (V2)

Three months after the baseline visit, the patient will go to the last control visit, to assess the incidence of VV recurrences during the follow-up period. The investigator will perform, as in all visits, the corresponding case history and examination and will record data on clinical manifestations. This visit does not include taking samples for laboratory tests. If the patient has filled in the home CRF on paper, she must deliver it during this last visit.

## 6.4 Description of the intervention

The intervention will be assigned to each patient according to the code assigned by order of inclusion in the study and will be used for randomisation. In the case of the control group, the specific treatment will be indicated after randomisation depending on the aetiology of the VV:

### 1) Candidal VV:

- a. Vaginal capsule with 150 mg of Boric Acid and Probiotics (*L. gasseri* and *L. rhamnosus*) plus prebiotics (1 capsule/24h for 1 week)
- b. Clotrimazole vaginal tablet 100 mg/24h, 6 days (Gine-Canesten®)

### 2) Bacterial VV:

- a. Vaginal capsule with 150 mg of Boric Acid and Probiotics (*L. gasseri* and *L. rhamnosus*) plus prebiotics (1 capsule/24h for 1 week)
- b. Clindamycin vaginal suppository 100 mg/24h, 3 days (Dalacin®)

## **6.5 Randomisation**

Patients will be randomly assigned to two groups according to the product under study or control product (two interventions considered as standard clinical practice based on the suspicion of aetiology associated to the VV). Random assignment of patients will be implicit in the code that will be assigned to them consecutively in each centre at the time of inclusion. The proportion of patients will be 1:1 between the study group and control group. Random lists will be generated with a software using blocks with up to three repetitions of the same treatment.

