### **1.11 Study design**

Multicentric, Open, Prospective, Drug-controlled Randomised Clinical Trial.

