### *6.2.2 Exclusion criteria*

- Symptoms (high suspicion) compatible with infection due to *Chlamydia trachomatis*, *Trichomona vaginalis*, *Neisseria gonorrhoeae* or *Herpes simplex*.
- Use of antifungal or probiotic agents during the last 2 weeks prior to the study.
- Patients who are receiving any other treatment with probiotics, vitamin complexes that may significantly interfere with the study assessments.
- Pregnant patients.
- Patients who may become pregnant (if there is a reasonable doubt about the possibility of pregnancy at the time of inclusion or during the study a blood pregnancy test will be performed to rule out this possibility).
- Patients who are menstruating at the time of inclusion.
- Breast-feeding patients.
- Immunocompromised patients.
- Patients who, based on the investigator's criteria, are not expected to complete the follow-up.

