## **9.6 CRF records and reports**

The investigator must ensure the accuracy, completion and relevance of the data communicated to the sponsor in the CRF and in all the reports requested. The data will be recorded in an online CRF to which only the investigator will have access through a user and password, both of which will be personal and non-transferable. All data obtained will be stored in an electronic file restricted to the staff of each centre and for which the principal investigator will be responsible.

Any change or correction to a CRF must be requested to the CRO responsible for monitoring, Clever Instruments S.L., by contacting the person responsible for the *data management* designated by the study sponsor. Changes must be documented and the investigator must keep records of changes and corrections.

The investigators or the institution must keep the CT documents, as required by applicable regulations. The investigator or institution must take measures to prevent the accidental or premature destruction of these documents.

At the request of the monitor, auditor, ERC or regulatory authority, the investigator/institution must have all records related to the CT available.

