### **10.2 CT sample, product or treatment labelling**

As this is an open study, products administered to patients will not have any special labelling and will be labelled in the same way as they are usually on the market.

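### In this open trial section 6.5 leaves the next allocation partly predictable, so selective enrolment is possible; how much depends on how the list rule is read

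*Combined protocol and SAP*

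**What the plan says.** Section 1.11 describes a "Multicentric, Open, Prospective, Drug-controlled Randomised Clinical Trial". Section 10.2 adds that "products administered to patients will not have any special labelling", so the centre can see what each patient receives.

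Section 6.5 says that the random assignment is "implicit in the code that will be assigned to them consecutively in each centre at the time of inclusion". Section 6.3.1 likewise makes assignment random "depending on the previously-established code that will be assigned to each patient". On the list itself, section 6.5 states "The proportion of patients will be 1:1 between the study group and control group" and "Random lists will be generated with a software using blocks with up to three repetitions of the same treatment".

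Section 6.4 differs on the level of the list: it ties the code to the order in which patients enter the study and does not mention centres.

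The gynaecologist chooses the patients (6.3.1), by consecutive sampling. One exclusion in 6.2.2 is a judgement: patients who, in the investigator's view, "are not expected to complete the follow-up". Section 6.3.3 places consent, the eligibility check, the baseline assessment and sampling before the product is handed over.

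No section says who holds the list. None mentions central release, envelopes or any other way of hiding the next code.

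**The concern.** Randomisation protects the comparison only if the person deciding whether to invite a patient cannot foresee her arm. Here past allocations are visible, the list rule is printed, and the same clinician invites patients and applies a discretionary exclusion. If milder or more promising cases are invited when one arm is expected, the groups differ at entry.

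The main analysis in section 8.2 is an unadjusted t or Mann–Whitney test on symptom scores about two weeks after treatment. A difference in prognosis at entry would pass straight into that result.

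**Working it through.** The plan gives no figure for predictability, and the minimum of 50 patients in section 6.8 comes without inputs, so there is nothing to reproduce.

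**Inputs from the documents.** 1:1 allocation; 50 patients, so about 25 per arm; at most three repetitions of a treatment.

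**Assumptions.** Five centres of ten (recruitment is competitive under 6.3.1, so no number per centre is fixed). No true effect, outcome SD 1. The investigator enrols patients whose prognosis is shifted by +η SD when the study arm is expected, by −η when control is expected, and not at all otherwise.

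**Formulas.** Let g be the proportion of allocations guessed correctly, counting no guess as one half.
- Bias = 2η(2g − 1), in SD units.
- Standard error of the difference = √(2/25) = 0.28 SD.
- Test size: simulation of the two-sided 5% t test (4,000 to 6,000 runs), with the noncentral t as a check.

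**Reading A: no more than three alike in a row.** An exact chain (fair coin, forced switch after three alike) makes 10.8% of allocations certain over ten patients, and 1 in 7 in the long run. g = 0.5 + 0.108/2 = 0.554. At η = 0.25, bias = 2 × 0.25 × 0.108 = 0.054; simulation gives 0.056.

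**Reading B: blocks of six (three of each).** The guesser names the arm with more places left.
- Correct guesses by position: 0.5 + 0.6 + 0.6 + 0.7 + 0.7 + 1.0 = 4.1 of 6 (68.3%).
- Certain allocations: 0.1 at position 4, 0.4 at position 5, 1 at position 6. That is 1.5 of 6, or 25% of a complete block.
- A centre of ten has one full block and four places of the next. g = (4.1 + 2.4)/10 = 0.65, and (1.5 + 0.1)/10 = 16% are certain.
- Bias at η = 0.25: 2 × 0.25 × 0.30 = 0.15.

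**Reading C: mixed blocks of 2, 4 and 6.** Guessing the lagging arm is right in 69% of cases. Only about 3% of allocations are certain if the order of sizes is unknown. Bias at η = 0.25: 2 × 0.25 × 0.38 = 0.19.

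**Reading D: one trial-wide list (section 6.4).** A guess from one centre's history is right in about 52% of cases. Bias at η = 0.25: 2 × 0.25 × 0.04 = 0.02.

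| Reading | g | Bias, η = 0.25 | Test size | Bias, η = 0.5 | Test size |
|---|---|---|---|---|---|
| A. Run cap of three | 55% | 0.06 | 5–6% | 0.11 | 6–7% |
| B. Blocks of six | 65% | 0.15 | 7–8% | 0.30 | about 16% |
| C. Mixed 2/4/6 | 69% | 0.19 | 9–10% | 0.38 | about 23% |
| D. Trial-wide list | 52% | 0.02 | about 5% | 0.04 | 5–6% |

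At η = 0.25 the noncentral t gives 5.4%, 8.1%, 10.1% and 5.1%, in line with the simulations.

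**Would varied blocks within centre be enough?** No. For sizes 4, 6 and 8 the guess rate is still about 66%. Varying the sizes reduces certain allocations but not average guessing.

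**The case against.** The plan has safeguards. Sampling is meant to be consecutive, and consent, eligibility and the baseline assessment come before hand-over. These help, but no screening log is described to verify consecutive sampling, and neither step hides the next code from someone deciding whom to invite.

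The wording of 6.5 is ambiguous, and under the run cap the effect is close to negligible. That stands, and it is why the size must be given as a range. It does not remove the defect: every within-centre reading beats a coin toss. If 6.4 governs, the problem nearly disappears; the documents do not settle this.

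This is a pilot of about 50, with a standard error of 0.28 SD, larger than any bias computed at η = 0.25. Patients may also change arm on request (6.2.3, 6.3.3), which weakens the motive to steer entry. Both points limit the weight of the finding. The main objective is still a comparison of effectiveness.

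The documents do not state that every investigator knows all past allocations in the centre. CRF access is personal, although the stored data are restricted to centre staff (9.6). An investigator who knows only some of them would guess less well.

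A reader might infer that centres hold the list and know every arm in advance. The bias would then be 2η = 0.5 SD at η = 0.25, with about 42% false rejections in the favoured direction. The plan does not say this. An arm implicit in a code may mean only that the code points to a list.

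A reader might also infer that no analysis could repair selection. That goes too far: signs, symptoms and the Sobel score are recorded at baseline, and adjusting for the score removes the measured part. It cannot remove selection on unmeasured prognosis.

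**Conclusion.** The point holds as a weakness in concealment. Followed as written, sections 6.3.1 and 6.5 let investigators partly predict the next arm, so selective enrolment is possible. The documents do not show that it occurred or was intended.

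With lists within centre and a shift of 0.25 SD, the bias is about 0.06 to 0.19 SD and the test size runs from 5–6% to 9–10%. At 0.5 SD the bias is about 0.11 to 0.38 SD. A trial-wide list brings it to about 0.02 SD at the smaller shift. The shift, the centre sizes and full knowledge of past allocations are assumptions. It should be corrected before the first patient, because the remedy is cheap.

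**What to change.** In section 6.5:
- State the level of the list and make section 6.4 agree.
- Remove the repetition rule from the text that sites see. Have the CRO hold a list with undisclosed, randomly varied block sizes.
- Release each allocation through the online CRF of section 9.6 ("The data will be recorded in an online CRF") only after consent, eligibility and the baseline scores are saved.
- Use patient codes that do not carry the arm.
- Keep a log of eligible patients who were not enrolled, so that consecutive sampling can be checked.

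The cost is an allocation function in the online CRF, which section 9.6 describes only for recording data.

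A trial-wide list is an option, since it nearly removes guessing from a centre's history. Its price is balance within centres: in simulation with mixed blocks, about 29% of centres of ten end at 7:3 or worse, against none with blocks of six within centre. The sponsor should weigh that.

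Adjusting the main comparison for the baseline score is a useful complement, but does not replace concealment.

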## **6.6 Concomitant treatments**

The existence of concomitant treatments will be recorded. Only treatments that can influence the trial results will be reason for withdrawal of the product (*section 6.2.4*).

## **6.7 Compliance with the intervention**

Compliance with the indicated intervention will be checked with the data recorded by the patient in the home CRF, with direct questions during the second visit (first control visit) and empty blisters returned by the patient.

## **6.8 Pre-determination of sample size**

A minimum of 50 patients are expected to be distributed between the study group (boric acid 150 mg, *L. gasseri*, *L. rhamnosus*) and control group (Clotrimazole 100 mg or Clindamycin 100 mg).

## 7 VARIABLES AND MEASURING INSTRUMENTS

### 7.1 Main assessment variables

- Presence and severity of clinical signs/symptoms associated to VV that the patient presents.
- Sobel score: Semi-quantitative scale where itching, erythema, oedema and stinging are indicated from 0 to 3: Absent (0), mild (1), moderate (2), severe (3).
- Vaginal pH (to be determined by placing a vaginal discharge sample in contact with reactive pH indicator strips).
- Fresh vaginal smear (presence of “*clue cells*” or hyphas).
- Vaginal discharge sample culture.
- *Lactobacillus spp.* count in vaginal discharge.
- Relevant gynaecological history (including previous VV episodes).
- Compliance with the treatment and the gynaecologist’s recommendations.
- Adverse Events.

### 7.2 Secondary assessment variables

- Socio-demographic data (age, marital status, etc.).
- Anthropometric data (height, weight, BMI).
- Relevant clinical history.
- Gynaecological history (surgery, STD, etc.).
- Current gynaecological situation (menopause, parity, stable partner, use of contraceptive methods).

### 7.3 End points

- Number of patients with VV recurrence during the follow-up period in each treatment group (incidence of recurrences after 3 months).
- Number of patients with resolved symptoms in each group 2 weeks after finishing the treatment.
- Changes in vaginal pH level in each group.
- Number of patients with “*clue cells*” or hyphas in the fresh smear.

- Profile and proportion of pathogen isolation in culture.
- Increase in the population of *Lactobacillus spp.* post-treatment.
- Rescue success rate in different scenarios.
- Relationship between compliance and treatment effectiveness.
- Relationship between compliance and recurrence after 3 months.
- Percentage of cases with good treatment tolerability.
- Rate of adverse events.
- Treatment tolerability.
- Proportion of patients with mixed infections (VC + BV).

## **8 STATISTICAL ANALYSIS**

All data will be analysed using the SPSS-Windows statistical package.

### **8.1 Descriptive statistics**

Descriptive statistics will be made of all the variables included in the CRF.

Categorical variables will be presented in the form of lists of frequencies and proportions. For quantitative variables (continuous or ordinal), central tendency (mean, medium, mode) and dispersion indices (standard deviation and maximum and minimum values) will also be presented.

### **8.2 Objectives of the study**

The analysis of the main objective will focus on the comparison of the effectiveness of the product under study (boric acid + *L. gasseri* and *L. rhamnosus*) and that of the control treatment with solid vaginal forms, according to the usual clinical practice (clotrimazole or clindamycin) and assessed according to the patient's clinical symptom scores (VAS, Sobel score) approximately 2 weeks after the end of the treatment. To do this, T tests for independent samples or non-parametric Mann–Whitney U tests will be used.

For the secondary objectives, the level of restoration of vaginal flora will be assessed by comparing the *Lactobacillus* count in baseline discharges and 2 weeks after treatment through T tests for related samples or non-parametric

Wilcoxon or McNemar tests. The incidence of recurrences/relapses at 3 months will be studied by means of proportion comparison tests (Pearson's chi-squared test). The characterisation of the different symptomatic and microbiological profiles of VV, as well as the tolerability, compliance and adverse events, will be analysed through descriptive statistics.

The possibility of carrying out additional analyses, depending on the results, with the relevant statistical tests in each case is not ruled out.

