## 2 INTRODUCTION AND JUSTIFICATION OF THE STUDY

Female lower genital tract infections are classified according to the primary location of signs and symptoms, theoretically distinguishing between vulvitis, vaginitis and endocervicitis. However, in practice, the inflammatory process is not usually limited to a single location, so in most patients it is manifested as vulvovaginitis (VV).

VV, which can affect both the vaginal mucosa and vulvar skin, is typically associated to symptoms and discomfort such as leukorrhea, itching, stinging, dysuria and, in some cases, dyspareunia. Most of these symptoms have an infectious origin, which is why their standardised approach involves the use of antifungal and/or antibiotic treatments.

According to different sources, VV represents more than one third of gynaecological consultations. Although most symptomatic episodes are effectively controlled with the different therapeutic alternatives available, the identification of pathogens resistant to the typically-used treatments raises the need to look for new alternatives.

It is estimated that 20-25% of VV are caused by different yeast species belonging to the *Candida sp* family, with the most frequent genus being *C. albicans* (more than 80% of cases). Furthermore, bacterial vaginosis (BV), which causes 40-50% of VV, is associated with different microorganisms such as *Gardnerella vaginalis*, *Mycoplasma*, *Bacteroides*, *Mobiluncus*, *Peptostreptococcus*, among others.

Most of these microorganisms are part of the vaginal flora without clinically manifesting themselves. Evidence suggests that a change in the flora's balance, particularly in the population of acidifying bacteria in the vaginal environment such as *Lactobacillus*, influences the growth of another type of microorganisms that finally cause the patient to become symptomatic.

Recurring forms, more typical in the case of candidiasis ( $\geq 4$  episodes/year), usually occur during the 3 months after treatment. The most accepted theory to explain this phenomenon is related to the persistence of the pathogen in the

vagina, corroborated by the isolation of forms with the same karyotype in recurrences.

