## **6.2 Study population**

### *6.2.1 Inclusion criteria*

- Women  $\geq$  18 years of age.
- Women with clinical manifestations of infectious VV.
- Women who agree to participate by signing the informed consent form.

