### *6.2.3 Rescue criteria*

In cases where the patient requires "rescue treatment", the treatments will be crossed. In the event of changing treatment group (crossover), the patient will be considered to be back at V0 and the tests/examinations corresponding to the baseline visit will be repeated.

The patient will change group to receive alternative treatment in the following cases:

- Patient with hypersensitivity to the first assigned treatment.
- Worsening of symptoms within 3-4 days of starting the assigned treatment.
- Evidence or indications of lack of effectiveness after the first assigned treatment.
- Patient who demonstrates a willingness to change treatment.
- In cases where the perceived lack of effectiveness is associated with a suspected mixed aetiology infection (candidal and bacterial):
  - If they are in the control group, they will be changed to the treatment under study (boric acid + *L. gasseri* and *L. rhamnosus*).
  - If they are in the study group, they will be changed to the antifungal treatment (Gine-Canesten®; Clotrimazole 100 mg). If this treatment fails, BV will be treated with antibiotic treatment (Dalacin®; Clindamycin 100 mg).

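### The main Sobel comparison leaves out the Sobel score already recorded at V0, which costs precision against the planned t test if V0 and V1 scores correlate above about 0.15

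*Combined protocol and SAP*

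**What the plan says.** Section 8.2 bases the main objective on symptom scores (VAS and Sobel) about 2 weeks after the end of treatment. The method is given in one sentence: "To do this, T tests for independent samples or non-parametric" Mann-Whitney U tests. No covariate, regression model or change score is named for this comparison.

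The V0 value exists. Section 6.3.3 has the investigator record, at inclusion, signs and symptoms ("stinging, itching, erythema, oedema, abnormal vaginal discharge, etc.) and the *Sobel score"), and section 6.3.5 repeats the clinical examination at V1. Section 7.1 describes the Sobel score as a "Semi-quantitative scale where itching, erythema, oedema and stinging are indicated from 0 to 3", without saying whether the four items are summed.

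Section 6.2.1 admits "Women with clinical manifestations of infectious VV" and sets no minimum score. Section 6.8 plans a minimum of 50 patients, and section 6.5 allocates them 1:1. Section 8.2 closes by leaving further analyses open, depending on the results.

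**The concern.** Because entry needs symptoms but no minimum severity, V0 Sobel scores can vary between patients and, by chance, between arms. If V0 severity predicts V1 severity, an unadjusted comparison leaves that predictable part in the error term. It also has no agreed way to deal with one arm starting out worse. With about 25 patients per arm the interval for the main comparison is already wide, so any precision available from data in hand matters.

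Timing also matters. The only opening for another analysis is the results-dependent sentence at the end of section 8.2. An adjustment brought in by that route, after the outcomes are seen, would be open to the charge that it was chosen for its result.

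**Working it through.** **No figure to reproduce.** Section 6.8 gives a minimum of 50 with no alpha, power, effect size or SD. The check therefore works in SD units of the V1 score, with a two-sided 5% level as an assumption.

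**Inputs.** n = 25 per arm (sections 6.8 and 6.5), all assumed evaluable at V1. The V0–V1 correlation r is not in the documents; it is an assumption, shown from 0 to 0.7.

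**Unadjusted t test.** The 95% CI half-width is t(48) × √(2/25) = 2.011 × 0.283 = 0.57 SD. The difference detectable with 80% power is 0.81 SD (noncentral t).

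**ANCOVA with V0 Sobel, against the t test.** For one covariate and normal data, the variance ratio, including the cost of estimating the slope, is (1 − r²) × [1 + 1/(2n − 4)] = (1 − r²) × 47/46. The half-width is t(47) × √(2/25 × ratio), and the equivalent unadjusted total is 50/ratio.

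| r | variance ratio | half-width (SD) | equivalent unadjusted total |
|---|---|---|---|
| 0 | 1.022 | 0.58 | 49 |
| 0.1 | 1.012 | 0.57 | 49 |
| 0.3 | 0.930 | 0.55 | 54 |
| 0.5 | 0.766 | 0.50 | 65 |
| 0.7 | 0.521 | 0.41 | 96 |

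Break-even is where (1 − r²) × 47/46 = 1, so r = √(1/47) = 0.146. Simulation with normal scores agrees with these ratios.

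**Larger trial.** Section 10.1 provides product for 70 patients. If that meant 35 per arm (an assumption, as the text is unclear), the unadjusted half-width is 0.48 SD and the ratios at r = 0.3, 0.5 and 0.7 are 0.924, 0.761 and 0.518.

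**Chance imbalance.** The difference in mean V0 between arms has SD √(2/25) = 0.283 in V0 SD units. It is at least 0.3 SD with probability 29% and at least 0.5 SD with probability 8%. At r = 0.5, the t test's type I error given the imbalance is 2.4% at none, 5.3% at 0.3 SD and 10.5% at 0.5 SD. ANCOVA stays near 5% at each. Averaged over randomisations, the t test is at 5%.

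**Floor at 0.** A floor is plausible. Section 2 says "most symptomatic episodes are effectively controlled with the different therapeutic alternatives available", and section 7.3 lists as an end point "Number of patients with resolved symptoms in each group 2 weeks after finishing the treatment". Simulation, assuming a 0–12 sum, gives these ANCOVA-to-unadjusted variance ratios for the difference in means at latent r = 0.3, 0.5 and 0.7:
- half of V1 scores at 0: 0.952, 0.825, 0.634
- 70% at 0: 0.967, 0.866, 0.720

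**Against Mann-Whitney.** The formula above does not apply to the rank test, so power was simulated on the same floored scale. With 70% of control scores at 0 and the study arm 0.8 latent SD better, Mann-Whitney had 47% power against 43% for ANCOVA at latent r = 0.3, and 49% against 46% at r = 0.5. Monte Carlo error is about 1 point, so the gap at r = 0.5 is small. ANCOVA was ahead at r = 0.7, and in every case where the study arm was the worse one.

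**The case against.** The strongest reply is that the planned test is sound and the benefit cannot be sized. Nothing in the documents places r near 0.5. At r = 0.2 the variance falls by only 2%, and with 70% of scores at 0 and latent r = 0.3 by 3%. A pilot with no stated precision target misses no target. This stands, and it limits how strongly the point can be put.

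Several stronger readings are tempting, and the documents do not support them:

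- **That the main test is biased or has an inflated error rate.** It does not. The 10.5% applies only given a 0.5 SD imbalance; in about 71% of randomisations the imbalance is below 0.3 SD and the test is at or below roughly nominal.
- **That the 0.15 threshold covers both planned tests.** It is derived for the t test only. Latent r = 0.3 with 70% zeros is an observed correlation of about 0.23, above the threshold, yet Mann-Whitney did slightly better there when the study arm was better.
- **That the same holds for VAS.** Section 6.3.3 does not list VAS at V0, and section 7.1 does not list it among the variables.
- **That the Lactobacillus analysis is a precedent.** Section 8.2 compares the "count in baseline discharges and 2 weeks after treatment through T tests for related samples", which is a before-after test and not a baseline-adjusted comparison of arms.
- **That any later adjustment must be data-driven.** Section 9.4 provides for amendments. One made before outcome data are examined would not be.

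**Conclusion.** The point holds as a matter of efficiency, not of validity. The main Sobel comparison sets aside a baseline value already collected and prespecifies no handling of chance baseline imbalance. Against the t test, the trade is at most about 2% more variance if V0 is uninformative, for 7%, 23% or 48% less at r = 0.3, 0.5 or 0.7.

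These figures rest on an assumed correlation, near-normal scores and 25 evaluable patients per arm. A floor at 0 reduces the gain, and under a heavy floor with low to moderate r the rank test may match ANCOVA or be a few points of power better. Severity lies between optional and should.

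**What to change.** In section 8.2, prespecify as the main Sobel analysis an ANCOVA of the V1 score on randomised arm and V0 Sobel score, reporting the adjusted difference with its 95% CI. Two details need stating:

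- The covariate is the V0 score from first randomisation. Under section 6.2.3, after crossover "the tests/examinations corresponding to the baseline visit will be repeated", and section 6.3.5 then treats that visit as a new V0; this later value must not replace the first.
- Patients are analysed by randomised arm.

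Because a floor is likely, add a proportional-odds model with the same terms as a fixed sensitivity analysis, not as an alternative to switch to, and keep the unadjusted test as supportive. A change score is not a substitute: with equal SDs its variance is 2(1 − r) times the unadjusted one, so it helps only above r = 0.5.

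The cost is analysis wording only, with no new field, patient or visit. It uses one degree of freedom, adds at most about 2% to the variance against the t test, and may lose a few points of power against Mann-Whitney under a heavy floor. Which outcome value to use for patients who cross treatments is a separate question, not settled here.
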